F11. Neurological evaluation by a nurse using the Glasgow Coma Scale post revascularization treatment

1-No 2-Yes 3-Not applicable 99-Missing data

F12. Result of Glasgow Coma Scale post revascularization treatment: _____

F13. Shoulder pain evaluation by the physiotherapist

1-No 2-Yes 3-Not applicable 99-Missing data

F14. Presence of shoulder pain

1-No 2-Yes 3-Not applicable 99-Missing data

F15. Result of first shoulder pain evaluation: _____

F16. Shoulder pain re-evaluation by physiotherapist

1-No 2-Yes 3-Not applicable 99-Missing data

F17. Result of second shoulder pain evaluation: _____

G. Complications during hospitalization

G1. Intracranial hemorrhage  1-No  2-Yes  99-Missing data	G2. Urinary tract infection  1-No  2-Yes  99-Missing data
G3. Aspiration pneumonia  1-No  2-Yes  99-Missing data	G4. Other pneumonia (nosocomial, ventilator-associated, etc.) Specify: _____  1-No  2-Yes  99-Missing data
G5. Malnourishment  1-No  2-Yes  99-Missing	G6. Convulsions  1-No  2-Yes  99-Missing data
G7. Deep vein thrombophlebitis  1-No  2-Yes  99-Missing data	G8. Depression  1-No  2-Yes  99-Missing data
G9. Temperature increase  1-No  2-Yes  99-Missing data	G10. Anxiety  1-No  2-Yes  99-Missing data
G11. Pulmonary embolism  1-No  2-Yes  99-Missing data	G12. Gastrointestinal bleeding  1-No  2-Yes  99-Missing data
G13. Shoulder subdislocation  1-No  2-Yes  99-Missing data	G14. Contracture  1-No  2-Yes  99-Missing data

H. Discharge / Transfer

H1. Death  1-No  2-Yes  99-Missing data
H2. Date and time of death DD/MM/YYYY ____ / ____ / ____ HH: MIN ____ : ____
H3. Short stay discharge  1-No  2-Yes  3-Not applicable  99-Missing data
H4. Date and time of short stay discharge DD/MM/YYYY ____ / ____ / ____ HH: MIN ____ : ____
H5. Date and time of stroke unit discharge

DD/MM/YYYY ____ / ____ / ____ HH: MIN ____ : ____	
H6. Date and time of intensive care unit discharge DD/MM/YYYY ____ / ____ / ____ HH: MIN ____ : ____	
H7. Presence in the record of functional independence evaluation using modified Rankin Scale (mRS)  1-No  2-Yes  3-Not applicable  99-Missing data	
H8. Clinician performing the functional independence evaluation using modified Rankin Scale (mRS) in the record  1-Nurse  2-Neurologist  3-Occupational therapist  4-Other: _____  99-Missing data	
H9. mRS result at discharge: _____	
H10. Anticoagulant prescribed at discharge  1-No  2-Yes  3-Not applicable  99-Missing data	
H11. Lipid-lowering medication prescribed at discharge  1-No  2-Yes  3-Not applicable  99-Missing data	
H12. Antiplatelet prescribed at discharge  1-No  2-Yes  3-Not applicable  99-Missing data	
H13. Hypertensive prescribed at discharge  1-No  2-Yes  3-Not applicable  99-Missing data	
H14. Hypoglycemic prescribed at discharge  1-No  2-Yes  3-Not applicable  99-Missing data	
H15. Discussion with patient about targeted goals for discharge  1-No  2-Yes  3-Not applicable  99-Missing data	
H16. Individualized intervention plan developed with patient and caregivers  1-No  2-Yes  3- Not applicable  99-Missing data	
H17. Therapeutic nursing plan developed by nurse with patient and caregivers  1-No  2-Yes  3- Not applicable  99-Missing data	
H18. Beneficiary assistant work plan developed by nurse	

 1-No	 2-Yes	 3- Not applicable	 99-Missing data
H19. Patient's walking program developed by nurse or interdisciplinary team			
 1-No	 2-Yes	 3- Not applicable	 99-Missing data
H20. Transfer at discharge			
 1-Return to place of residence	 2- Outpatient rehabilitation services		
 3- Inpatient rehabilitation	 4- Long-term care center		
 5- Palliative care	 6-Not applicable		
 7- Other: _____			
H21. Referral regarding secondary prevention			
 1-No	 2-Yes	 3-Not applicable	 99-Missing data
H22. Clinician who referred to secondary prevention services			
 1-Nurse	 2-Neurologist	 3-Other: _____	
 99-Missing data			
H23. Readmission within 30 days for stroke-related issue			
 1-No	 2-Yes	 3-Not applicable	 99-Missing data

I. Discharge education

I1. Information on modifiable risk factors			
 1-No	 2-yes	 3-Not applicable	 99-Missing data
I2. Information on stroke symptoms			
 1-No	 2-Yes	 3-Not applicable	 99-Missing data
I3. Information on the urgency of consulting in the presence of stroke symptoms			
 1-No	 2-Yes	 3-Not applicable	 99-Missing data
I4. Information on post-stroke follow-up			
 1-No	 2-Yes	 3-Not applicable	 99-Missing data
I5. Information on prescribed medications			
 1-No	 2-Yes	 3-Not applicable	 99-Missing data
I6. Information on available community resources			

 1-No	 2-Yes	 3-Not applicable	 99-Missing data
17. Professionals providing information to patient and caregivers			
 Nurse	 Physiotherapist	 Speech therapist	
 Neurologist	 Occupational therapist	 Nutritionist	
 Autre : _____		 99-Missing data	

APPENDIX 3

Collection sheet on hospital characteristics

A. Hospital center	
A1. Collection data DD/MM/YYYY	____ / ____ / ____
A2. Center	
B. Geographic and demographic characteristics	
B1. Type of designation	B2. Description of center's mission and role in relation to type of designation
 1-Primary  2-Secondary  3-Tertiary	
B3. Geographic distribution (regions served)	
 Mauricie	
 Centre du Québec	
 Estrie	
 Montreal	
 Laval	
 Lanaudière	
 Montérégie	
 Other: _____	
B4. Population served (approximate number of persons):	_____
B5. Total annual average number of patients admitted:	_____
B6. Total annual average number of patients admitted with a diagnosis of ischemic stroke:	_____
B7. Total number of short-term beds:	_____

B8. Total number of beds on stroke unit or reserved for stroke patients: _____
B9. Annual number of satisfactions and complaints related to patients' stay in stroke unit: Satisfactions: _____ Complaints: _____
B10. Annual number of incident/accident reports (e.g., medication errors, falls, etc.) related to patients' stay in stroke unit: _____
B11. Annual number of restraint and seclusion measures related to patients' stay in stroke unit: _____
B12. Number of continuous observations of a stroke unit patient by a patient care assistant (PCA), a security guard, or a member of the family or the establishment: _____

C. Characteristics of human resources	
C1. Type and number of clinicians available in neurovascular department/neurology (stroke)	C2. Interdisciplinary (multidisciplinary) meetings  No  2-Yes
 Nurse technician: _____	C3. Frequency of multidisciplinary meetings Frequency: _____
 Nurse clinician: _____	C4. Progression of multidisciplinary meetings _____
 Nurse specialist: _____	_____
 Nursing assistant: _____	_____
 Patient care assistant (PCA): _____	_____
 Occupational therapist: _____	_____
 Physiotherapist: _____	_____
 Speech therapist: _____	_____
 Nutritionist: _____	_____

Kinesiologist: _____
 Doctor: _____
 Internist: _____
 Neurologist : _____
 Neurointerventionniste: _____
 Other: _____

C5. Ratio patients/clinicians

Ratio	Day	Evening	Night
Patients/Nurse			
Patients/Nursing assistant			
Patients/PCA			
Patients/Occupational therapist			
Patients/Physiotherapist			
Patients/Speech therapist			

C6. Mandatory overtime on stroke unit No Yes Frequency: _____

C7. Rate of staff turnover on stroke unit: _____

C8. Rate of absenteeism on stroke unit: _____

C9. Average number of years of experience

Clinicians	Day	Evening	Night
Nurse			
Nursing assistant			
Patient care assistant			
Occupational therapist			
Physiotherapist			
Speech therapist			

C10. Proportion of nurse technicians and of nurse clinicians (total number of nurses)

Nurse technicians: _____

Nurse clinicians: _____

D. Documentation and dissemination

D1. Clinical and organizational documentation in effect (protocols, procedures, prescriptions, health records, etc.)

D2. Action plans or projects designed for continuous improvement of quality of care and services

D3. Frequency and type of content regarding training offered to different clinicians

Frequency: _____

Content of training:

D4. Internal and external resources (material resources (organizational networking; policies, plans or programs in effect; service corridors and agreements, etc.)

D5. Methods of communication for transmitting information to the teams

E. Remote communities

E1. Percentage of remote communities with access to the Telehealth/Telestroke program which facilitates access to organized ischemic stroke care across the care continuum, notably evaluation of needs and delivery of care related to post-stroke rehabilitation.

Percentage: _____

Comments:

E2. Increase in percentage of Telehealth/Telestroke coverage of remote communities to support organized stroke care across the continuum of care in recent years

Percentage: _____ (YYYY)

Percentage: _____ (2021-2022)

Comments:

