3.1 Type of study

To meet the objectives of the research questions, a retrospective descriptive-correlational study will be conducted based on methods of collecting and analyzing quantitative data. The decision to conduct a retrospective study was made for two reasons: first, the nature of the data collected from records allows us to describe the current state of clinical and organizational practices during the length of patients' stay; and second, this type of study

May 2022

page 11 de 48

[name], [name], [name]

allows for the inclusion of a sample of patients hospitalized during a fixed six-month period. Finally, the feasibility of a retrospective study was considered within the context of a doctoral project with limited resources, time and budget.

In keeping with these considerations, the present study involves a multicentric investigation to take place in three differently designated Quebec hospitals in terms of stroke care. The choice of a multicentric study is based on using a larger sample of patients from different areas to obtain a broad overall view of clinical and organizational practice in stroke management in Quebec. In this study, the primary care center is a multi-vocational center including hospital care that is located in a remote area. The second participating center is a secondary care university hospital that plays an important role in the optimization of stroke care and services throughout its territory given its status as a regional center. The third hospital targeted by the study is a specialized tertiary care center which is nationally recognized for stroke treatment and performs the most thrombectomies in Quebec.

Having different and welldefined missions, these centers maintain an interdependent relation through the offer of proposed care and services. Notably, the patients from the primary care center requiring a thrombectomy are generally transferred to the tertiary center participating in this study to receive treatment. Additionally, although the tertiary care hospital is a thrombectomy center, the patients transferred there must also be returned to the secondary care referral center quickly after treatment to begin rehabilitation as early as possible. Since the majority of guidelines apply in all types of centers irrespective of where the patient is managed, each center must self-compare regarding the achievement of quality indicators.

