Proportion of post-stroke patients investigated for cardiac arrhythmia (electrocardiogram, heart monitor, telemetry, etc.)

Numerator: Number of post-stroke patients investigated for cardiac arrhythmia

Denominator: Total number of post-stroke patients

Indicator 12

Proportion of post-stroke patients screened for dysphagia within 4 hours following triage or within 24 hours following admission or prior to all oral intake of substances and liquids

Numerator 1: Number of post stroke patients screened for dysphagia within 4 hours following triage

Numerator 2: Number of post-stroke patients screened for dysphagia within 24 hours following admission

Numerator 3: Number of post-stroke patients screened for dysphagia prior to all oral intake of substances and liquids

Denominator: Total number of post-stroke patients

Indicator 13

Proportion of post-stroke patients evaluated for pressure sore risk and regularly evaluated to prevent these sores using a valid tool (Braden Scale)

Numerator: Number of post-stroke patients evaluated for pressure sore risk and regularly evaluated using a valid tool

Denominator: Total number of post-stroke patients

Indicator 14

Proportion of post-stroke patients neurologically evaluated using a valid scale (e.g., Canadian Neurological Scale [CNS], National Institutes of Health Stroke Scale [NIHSS])

Numerator: Number of post-stroke patients neurologically evaluated using a valid scale

Denominator: Total number of post-stroke patients

Indicator 15

Proportion of post-stroke patients screened or evaluated for risk of fall

Numerator: Number of post-stroke patients screened or evaluated for risk of fall

Denominator: Total number of post-stroke patients

Indicator 16

Proportion of post-stroke patients with complication of symptomatic intracranial hemorrhage following thrombolytic or endovascular therapy

Numerator: Number of post-stroke patients with complication of symptomatic intracranial hemorrhage following thrombolytic or endovascular therapy

Denominator: Total number of post-stroke patients given thrombolytic or endovascular therapy

Indicator 17

Proportion of post-stroke patients with one of the following complications during hospitalization: aspiration pneumonia, deep vein thrombosis, fever, pulmonary thromboembolism (PTE), shoulder subdislocation, urinary tract infection, contracture, malnourishment, depression/anxiety, gastrointestinal bleeding, convulsions (Result by type of complication)

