 4-Lipid-lowering medication	 5-Antiplatelet	 6-Other: <hr/>
 7-Other: _____	 8-Other: _____	 99-Missing data
C7. Covid-positive		
 1-No	 2-Yes	
 99-Missing data		

C8. First NIHSS evaluation (initial)  1-No  2-Yes  99-Missing data	C9. Initial NIHSS result: _____
C10. First modified Rankin assessment (initial mRS)  1-No  2-Yes  99-Missing data	C11. Initial mRS result: _____

D. Risk factors			
D1. Smoking  1-No  2-Yes  99-Missing data	D2. Physical inactivity  1-Yes  2-No  99-Missing data		
D3. Obesity  1-No  2-Yes  99-Missing data	D4. Poor nutrition  1-No  2-Yes  99-Missing data		
D5. Alcohol consumption  1-No  2-Yes  99-Missing data	D6. Drug use  1-No  2-Yes  99-Missing data		
D7. Arterial hypertension  1-No  2-Yes  99-Missing data	D8. Dyslipidemia  1-No  2-Yes  99-Missing data		
D9. Type 2 diabetes  1-No  2-Yes  99-Missing data	D10. Carotid stenosis  1-No  2-Yes  99-Missing data		
D11. Sleep apnea			

 1-No	 2-Yes	
 99-Missing data		

E. Patient flow / Time intervals				
E1. Date and time of arrival at triage		DD/MM/YYYY ____ / ____ / ____ HH: MIN ____ : ____		
E2. Date and time of admission to a short-term unit (regardless of unit) DD/MM/YYYY ____ / ____ / ____ HH : MIN ____ : ____				
E3. Admission to stroke care unit  1-No  2-Yes  3-Not applicable  99-Missing data				
E4. Date and time of admission to stroke care unit DD/MM/YYYY ____ / ____ / ____ HH: MIN ____ : ____				

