DD/MM/YYYY	____ / ____ / ____	HH: MIN	____ : ____
E24. Date and time of first oral administration			
DD/MM/YYYY	____ / ____ / ____	HH: MIN	____ : ____
E25. Presence of dysphagia			

 1-No	 2-Yes	 99-Missing data	
E26. Evaluation by a clinician in presence of dysphagia			
 1-No	 2-Yes	 3-Not applicable	
 99-Missing data			
E27. Referral to IFRU by a doctor			
 1-No	 2-Yes	 3-Not applicable	
 99-Missing data			
E28. Date and time of referral to IFRU			
DD/MM/YYYY	____ / ____ / ____	HH: MIN	____ : ____
E29. Admission to IFRU			
 1-No	 2-Yes	 3-Not applicable	
 99-Missing data			
E30. Date and time of admission to IFRU			
DD/MM/YYYY	____ / ____ / ____	HH: MIN	____ : ____
E31. CT carotid angiogram			
 1-No	 2-Yes	 3-Not applicable	
 99-Missing data			
E32. Date and time of CT carotid angiogram			
DD/MM/YYYY	____ / ____ / ____	HH: MIN	____ : ____

F. Evaluations

F1. Medical evaluation for cardiac arrhythmia			
 1-No	 2-Yes	 3-Not applicable	 99-Missing data
F2. Presence of cardiac arrhythmia			
 1-No	 2-Yes	 3-Not applicable	 99-Missing data
F3. Evaluation of pressure sore risk (Braden Scale) by the nurse			
 1-No	 2-Yes	 3-Not applicable	 99-Missing data

F4. Result of pressure sore evaluation (Braden Scale): _____

F5. Re-evaluation of pressure sore risk (Braden Scale) by the nurse

1-No 2-Yes 3-Not applicable 99-Missing data

F6. Evaluation of risk of fall by a nurse

1-No 2-Yes 3-Not applicable 99-Missing data

F7. Neurological evaluation by a nurse using the Canadian Neurological Scale

1-No 2-Yes 3-Not applicable 99-Missing data

F8. Result of neurological evaluation on the CNS: _____

F9. Neurological evaluation by the doctor using the NIHSS post revascularization treatment

1-No 2-Yes 3-Not applicable 99-Missing data

F10. Result of NIHSS post revascularization treatment: _____

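### Indicator 13 asks for regular pressure-sore re-evaluation, but the collection sheet holds one undated, uncounted re-evaluation item, so regularity cannot be measured and the result can depend on length of stay

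*Protocol*

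**What the plan says.** Appendix 1, Safety, Indicator 13 is "Proportion of post-stroke patients evaluated for pressure sore risk and regularly evaluated to prevent these sores using a valid tool (Braden Scale". Its two components are "Numerator: Number of post-stroke patients evaluated for pressure sore risk and regularly evaluated using a valid tool" and "Denominator: Total number of post-stroke patients". No interval or minimum number is attached to *regularly*, and no minimum stay is attached to the denominator.

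Appendix 2, section F, holds the matching fields: "F3. Evaluation of pressure sore risk (Braden Scale) by the nurse", then F4 for one Braden result, then "F5. Re-evaluation of pressure sore risk (Braden Scale) by the nurse". The codes printed under F5 are "1-No 2-Yes 3-Not applicable 99-Missing data". F3, F4 and F5 carry no date and no count. Section E of the same sheet, by contrast, records date and time for many single events, for example "E2. Date and time of admission to a short-term unit (regardless of unit". With the discharge time in H4, length of stay can be derived.

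Section 3.5 says that indicators will be described for each centre and for all three together. Those with extensive data will be dependent variables in regressions on patient characteristics. Section 3.1 says that patients transferred to the tertiary centre "must also be returned to the secondary care referral center quickly after treatment".

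**The concern.** The definition and the data field do not match. The numerator needs a pattern of repeated evaluation across the stay, while the sheet stores whether at least one repeat occurred. A patient re-scored once in a long stay and a patient re-scored throughout get the same code.

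A record of at least one repeat also tends to become more likely the longer a patient stays, even when nursing practice is the same. If stays differ between centres, or with age or severity, part of any difference in Indicator 13 could reflect stay. This could distort the per-centre description and any regression on characteristics related to stay.

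The records are abstracted once. If the number and timing of scores are not taken down then, they can be recovered only by reopening the charts.

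**Working it through.** The protocol states no rate or target for Indicator 13, so there is no figure to reproduce. The check compares definition with field and then illustrates the size with assumed inputs.

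**1. Definition against field.**
- Needed for the numerator: first evaluation done, and re-evaluation done regularly.
- Held on the sheet: F3 for the first part; F5, a single item, for the second.
- Derivable: length of stay, from E2 and H4.
- Not derivable: number, spacing or timing of re-evaluations. *Regularly* therefore cannot be determined, whatever meaning is later given to it.

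**2. Dependence on stay.** Assume a constant probability *q* of a re-evaluation on each day after the first, and a stay of *L* days. Then P(F5 = Yes) = 1 − (1 − q)^(L − 1). Neither *q* nor *L* is in the documents, so a range is shown.

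| Stay (days) | q = 0.1 | q = 0.2 | q = 0.5 |
|---|---|---|---|
| 2 | 10% | 20% | 50% |
| 5 | 34% | 59% | 94% |
| 7 | 47% | 74% | 98% |
| 14 | 75% | 95% | 100% |
| 21 | 88% | 99% | 100% |

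For example, q = 0.2 and L = 5 give 1 − 0.8^4 = 0.59. The gradient is steep when re-evaluation is infrequent and nearly gone after the first few days when it is frequent.

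**3. A single repeat counted as regular.** Under the same model, the chance of exactly one re-evaluation in *L* days is (L − 1) × q × (1 − q)^(L − 2). For L = 21 and q = 0.1 this is 20 × 0.1 × 0.9^19 = 0.27, against P(Yes) = 0.88. So 0.27 / 0.88, about 31% of the Yes codes, would rest on one repeat in three weeks. At q = 0.2 it is 20 × 0.2 × 0.8^19 = 0.058 out of 0.99, about 6%.

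**4. Denominator.** Let *c* be the proportion achieving re-evaluation among patients for whom one was due, and *s* the share of stays too short for one to be due. If the short stays remain in the denominator without counting in the numerator, the reported rate is c × (1 − s). If they leave it, the rate is *c*. With an assumed c = 80%:
- s = 10%: 0.8 × 0.9 = 72%
- s = 40%: 0.8 × 0.6 = 48%
- short stays removed: 80% in both cases

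Two centres with equal practice could thus report 72% and 48%. This happens only if short stays are coded No, or coded Not applicable and still kept in the all-patients denominator. The protocol does not say when code 3 applies or whether it removes a patient.

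**The case against.** A reader might infer that short stays simply count as failures. The documents do not support that as fact. F5 has a Not applicable code, which is a natural home for a stay with no re-evaluation due. The all-patients denominator in Appendix 1 permits the unfavourable reading, but the protocol does not settle it.

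A reader might also infer that the tertiary centre is bound to look worse. Section 3.1 speaks only of patients transferred there, their share of the tertiary sample is not given, and no lengths of stay are reported. The same section says that each centre must compare itself with itself, and Section 3.5 specifies no test between centres for the descriptive objective. Distortion between centres is a risk, not a demonstrated result.

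Nor do the documents show that the indicator reflects stay more than nursing practice. The gradient comes from assumed probabilities and shrinks sharply as they rise. Section 3.5 limits regression to indicators with extensive data and allows confounders, so Indicator 13 may never be modelled. If it is, length of stay can be adjusted for.

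These points limit the consequences and leave the mismatch. Adjusting for stay cannot show how often a patient was re-scored. A statistical analysis plan could fix the handling of code 3, but it cannot create a count that was never abstracted.

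Scoring each centre only against its own written frequency would be a weak remedy. It sets up to three standards, and a laxer policy would score better. Section 3.4.3 and Appendix 3, item D1, collect protocols in general without naming a Braden frequency, and Section 8.2 notes gaps in written documentation on certain hospital characteristics.

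**Conclusion.** The point holds as a mismatch between definition and data. As written, Indicator 13 cannot distinguish one repeat evaluation from regular re-evaluation, and no later analysis can recover the difference without returning to the charts. That conclusion rests on the text of the two appendices alone.

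The dependence on stay is a reasonable expectation whose size is unknown. It assumes that chances to re-evaluate accumulate with time in hospital, and the percentages further assume a constant daily probability. The lowering of the rate by short stays is conditional on coding and denominator rules that the protocol leaves open. Any effect on centre descriptions or regressions is possible rather than shown. This is one of 29 indicators, but the correction is cheap before abstraction and costly afterwards.

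**What to change.** Before abstraction starts:

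1. Replace or supplement F5 with the number, or the dates, of Braden scores during the stay.
2. Report two results: (a) first evaluation done, from F3, over all patients; (b) re-evaluation. Part (a) needs no new field.
3. Report (b) relative to length of stay (E2 to H4, or to the death date in H2 where the patient dies in hospital), for example as scores per days of stay. Apply one measurement definition of *regularly* to all centres. Comparison with a centre's own written frequency, where one exists, can be a secondary description.
4. State that code 3 under F5 applies to stays with no re-evaluation due under that definition, and that these stays leave the denominator of (b).

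No clinical re-evaluation interval is proposed; the definition needed is one for measurement.

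The cost is one field on the sheet, a few sentences in Appendix 1, and a little more abstraction time per record.

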3.4 Tools and data collection

Data collection will begin once ethical approval is given (REB) and will be conducted using the health records of patients hospitalized during the 6 months preceding this approval. Archivists in each center in the study will provide randomly selected lists of the health records of patients meeting inclusion criteria. Data collected on each of the variables under study will be stored in a password-secured file. The complete list of clinical and organizational quality indicators in the scoping review is presented in Appendix 1. The data collection sheet on patients' characteristics and clinical and organizational quality indicators is given in Appendix 2.

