3.5 Projected statistical analyses

In response to the first research question, descriptive analyses will be conducted based on measurement of the clinical and organizational quality indicators identified in the acute phase. Medians and interquartile ranges, means and standard deviations and proportions will be used to describe performance of care and services for each center under study and comprehensively for all three centers. Additionally, a contextual description of each center will be presented using data collected on the hospitals' characteristics.

Results of the first objective will highlight indicators that do or do not meet the guidelines for quality of care for persons with ischemic stroke and their caregivers. For indicators presenting extensive data, regression analyses will be performed to identify the determinants likely to influence results regarding these indicators.

Dependent variables are clinical or organizational quality indicators, while independent variables correspond to the sociodemographic characteristics and clinical profile of patients with ischemic stroke. Type of regression analysis will vary consistent with the nature of the dependent variables (dichotomous or continuous) and their distribution (parametric or nonparametric tests).

A univariate regression analysis will first allow us to associate determinants (independent variables) with results for the indicators (dependent variables). Variables with a statistically significant association will then be introduced into a linear or logistic regression model. Additionally, these regression analyses will include

confounding variables that may also influence results from the measurement of clinical and organizational quality indicators. To be statistically significant, results must obtain a value of $p < 0.05$ and have a confidence interval of 95 %. All statistical analyses will be conducted using SPSS 28.0 software. Results will be presented comprehensively for the three centers; they may also be presented individually for the secondary and tertiary centers to see if the associations in them are similar or different. If the number of records in one of these hospitals is not enough for statistical power, the analysis will not be performed.

4. Consent process

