Numerator: Number of post-stroke patients with one or more of these post-stroke complications during hospitalization

Denominator: Total number of post-stroke patients

Indicator 18

Proportion of patients given a carotid Doppler test within 24 hours

Numerator: Number of post-stroke patients given a carotid Doppler test within 24 hours

Denominator: Total number of post-stroke patients

Effectiveness

Indicator 19

Proportion of patients who die from stroke in hospital within 7 days and within 30 days following admission

Numerator 1: Number of patients who die from stroke within 7 days following admission to hospital

Numerator 2: Number of patients who die from stroke within 30 days following admission to hospital

Denominator: Total number of ischemic stroke patients hospitalized or discharged from hospital

Indicator 20

Proportion of patients with severe disability at discharge (mRS 0-3) (Calculate proportion of patients for each modified Rankin score, mRS of 1 to 5.)

Numerator: Number of patients with a modified Rankin score (mRS) between 0 and 3 at discharge

Denominator: Total number of patients with a modified Rankin score recorded at discharge

Indicator 21

Proportion of patients with increased shoulder pain based on pain intensity score evaluated with a valid tool using reference data during hospitalization

Numerator: Number of post-stroke patients with increased shoulder pain based on pain intensity score evaluated with a valid tool

Denominator: Number of post-stroke patients with shoulder pain

Indicator 22

Proportion of patients readmitted to short-term hospital care for a stroke-related issue after discharge (post 30 days)

Numerator: Number of patients readmitted to short-term hospital care for a stroke-related issue within 30 days after discharge

Denominator: Total number of post-stroke patients re-hospitalized after discharge

Continuity

Indicator 23

Proportion of post-stroke patients prescribed an anticoagulant, lipid-lowering medication, an antiplatelet, an antihypertensive, or a hypoglycemic at discharge (Result per medication)

Numerator: Number of post-stroke patients prescribed an anticoagulant, lipid-lowering medication, an antiplatelet, an antihypertensive, or a hypoglycemic at discharge

Denominator: Total number of post-stroke patients prescribed one or more medications

Indicator 24

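### Indicator 18 counts carotid Doppler within 24 hours, but the collection sheet records only CT carotid angiogram, so its numerator cannot be computed

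*Protocol*

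**What the plan says.** Appendix 1 of the protocol lists 29 indicators with their numerators and denominators. Indicator 18, under Safety, is the "Proportion of patients given a carotid Doppler test within 24 hours". Its numerator repeats the same test and time limit, and its denominator is all post-stroke patients.

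Section 3.4 says that the sheet for patient characteristics and "clinical and organizational quality indicators is given in Appendix 2". For the carotid arteries, that sheet offers "E31. CT carotid angiogram" (yes, no, not applicable, missing) and "E32. Date and time of CT carotid angiogram". The only other carotid item is D10, carotid stenosis as a risk factor, which records neither a test nor a time.

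Two possible starting points for a time window are collected: "E1. Date and time of arrival at triage" and "E2. Date and time of admission to a short-term unit (regardless of unit)". Indicator 18 does not say which applies.

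Section 3.5 says what the indicator values are for: the results of the first objective will "highlight indicators that do or do not meet the guidelines".

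**The concern.** The definition and the instrument name different tests. A data collector who completes Appendix 2 faithfully will have nothing from which to count Doppler examinations. An analyst would then have to leave Indicator 18 blank, or fill it from E31 and E32 and so report CT angiography under the Doppler label.

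The indicator values are the main product of this study. They are to be described by center and overall and compared with guidelines, and some will become dependent variables in regressions (section 3.5). Section 8.1 also offers the method for reuse by other organizations. A mislabelled indicator would misstate practice at each center and pass the error on to anyone who adopts the sheet.

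**Working it through.** The protocol gives no figure to reproduce here. The check compares each definition in Appendix 1 with the fields in Appendix 2.

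**Indicator 18 (main point)**
- Needed for the numerator: Doppler done (yes/no), and its date and time.
- On the sheet: 0 of these 2 items.
- The word Doppler occurs nowhere in the protocol outside Indicator 18. Conversely, no indicator in Appendix 1 names CT carotid angiogram, so E31 and E32 feed no indicator as written.
- What the sheet does allow is the proportion with CT carotid angiogram within 24 hours of E1 or of E2. That is a different quantity.
- Time origin: Indicator 12 states its starting points (triage for 4 hours, admission for 24 hours). Indicator 18 states none.

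**Lesser mismatches (a broader or altered version can still be computed)**

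| Indicator | Definition requires | Sheet holds | Missing |
|---|---|---|---|
| 16 | Symptomatic intracranial bleed after thrombolysis or endovascular therapy | Treatment (C2, C3), any in-hospital intracranial bleed (G1) | Symptomatic or not |
| 4 | Time from triage to dysphagia screening with a valid tool | Triage time (E1), screening and its time (E22, E23) | Tool used |
| 19 | Death from stroke | Death and its date (H1, H2) | Cause of death |
| 21 | Increased shoulder pain on a valid tool | Two scores (F15, F17) | Tool used |
| 22 | Denominator of all re-hospitalized patients | Stroke-related readmission within 30 days (H23) | Other re-hospitalizations |

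For Indicator 16 the numerator is "Number of post-stroke patients with complication of symptomatic intracranial hemorrhage following thrombolytic or endovascular therapy". Symptomatic bleeds are a subset of treated patients with G1 = Yes, so the computed rate is equal to or above the defined rate. The protocol gives no figure from which to size the excess.

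For Indicator 4, the sheet names the instrument in other places (Braden in F3, the Canadian Neurological Scale in F7, NIHSS in F9), but not for dysphagia. Both Quebec results cited in the Introduction, 16 % and 65 %, count only screening with a standardized tool. If those shares held here, which is an assumption, 0.16 × 130 = 20.8 to 0.65 × 130 = 84.5 records would hold a qualifying screening, and the sheet could not show which. This is an illustration only. It does not say how many non-qualifying screenings E22 would let in, or how far the mean or median interval would move.

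**Cost of late repair.** Section 6.3 keeps patients traceable, so records can be reopened. If Doppler itself is wanted, Indicator 18 would mean reopening all of about 130 records. Indicator 16 would need only treated patients with G1 = Yes, and Indicator 4 only records with E22 = Yes.

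**The case against.** The strongest reply is that this is a labelling slip. E31 and E32 are the only carotid imaging items, they carry a yes/no and a time, and they match no other indicator, so they were probably meant to feed Indicator 18. The text also shows traces of translation and another slip on the same sheet: H13 asks about a hypertensive drug where Indicator 23 has an antihypertensive. That is plausible, but the protocol does not say so. If it is true, the indicator's wording is wrong and still has to be changed. What stands is that the repair may be as small as one reworded line, with no record reopened.

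It can also be said that section 8.2 foresees choosing priority indicators, and that section 3.3.2 provides a test phase. Section 8.2 drops no indicator by name, and the Introduction already calls the 29 the priority set. The test phase is described as timing the work per record and allowing adjustments. No check of indicators against the sheet is mentioned.

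A third reply is that coding rules for the lesser mismatches may sit in an analysis plan that is not available here. Such a plan could define what counts as symptomatic or as a valid tool, but it cannot supply a field that was never collected. The sheet does hold NIHSS and Glasgow scores after revascularization (F9 to F12), which bear on Indicator 16 but do not by themselves identify a symptomatic bleed. On Indicator 22 the objection is partly right. The definition is itself inconsistent, since the title's bracket reads as after 30 days while the numerator counts readmission within 30 days, and the denominator takes only re-hospitalized patients. The fault there is not only in the sheet.

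Finally, the reach is limited: one indicator of 29, in a descriptive study, with no sample size resting on it. That is fair and keeps the point below the most serious class.

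**Conclusion.** The concern holds. Indicator 18 cannot be computed as defined for any of about 130 records, because neither of its two required items is on the sheet and no text links Doppler to CT angiogram. This rests on Appendix 2 being the full collection sheet, as section 3.4 and the appendix title present it. The mismatches in Indicators 4, 16, 19, 21 and 22 are real but lesser, and the protocol does not allow their effect to be sized beyond the direction for Indicator 16. The point should be fixed, ideally before data collection. Which carotid test the indicator ought to measure is for the sponsor to decide.

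**What to change.** Reconcile Appendices 1 and 2 before collection starts.

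- **Indicator 18:** either add Doppler done (yes/no) with date and time to Appendix 2, or redefine the indicator as the carotid imaging that E31 and E32 record. In both cases state whether the 24 hours run from triage (E1) or from admission (E2).
- **Indicator 16:** add one symptomatic yes/no item beside G1 with a stated definition, or relabel the indicator as any in-hospital intracranial hemorrhage in treated patients.
- **Indicator 4:** add to E22 whether a standardized tool was used, and which.
- **Indicator 22:** settle the 30-day wording and the denominator in Appendix 1, then match H23 to them.
- **All patient-level indicators, including 19 and 21:** use the six-record test phase to confirm that each can be computed from the sheet as defined.

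For Indicators 18, 16 and 4 the cost is at most 2 + 1 + 1 = 4 fields, or 4 × 130 = 520 entries. Fewer are needed in practice, since the time, symptomatic and tool fields are filled only when the event occurred. The minimal version is one field (tool, at most 130 entries) and two wording changes. Indicators 19, 21 and 22 are not costed here. If collection has already finished, rewording Indicator 18 to match E31 and E32 still prevents a mislabelled result.
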